4. SUBJECT SELECTION

We aim to consent up to 100 women. Because we anticipate that approximately 20% will not meet eligibility criteria during the screening phase, this will achieve our accrual goal of 80 women (~40/treatment arm) who will complete the protocol and provide usable data for the acute primary outcomes. We also expect to have at least 72 women complete the 30-day follow-up period. These estimates derive from our experience with similar types of studies and populations.

Sources of recruitment: We will recruit study participants via several key resources that exist within our health system, including:

- RALLY, an online platform that serves as a resource for disseminating research opportunities within the Mass General Brigham (MGB) health system.
- The MGB-wide Research Patient Data Registry (RPDR), a research registry that allows investigators to query eligible participants based upon specified inclusion/exclusion criteria.
- Patient Gateway letters (identified via RPDR, described above). If we do not receive a response to our first letter within one week, we will send a second letter; if there is still no response, our third and final letter will be sent at least two weeks after the first. Following that, we will call up to three times, and if we are still unable to reach the patient, we will mark them as not interested. Patients who opted out will be filtered out of the recruitment list and they will not be sent the Research Invitation. The PI will conduct ongoing monitoring of patient responses to ensure that our selection criteria are identifying the right patients, and complaints about this method of recruitment will be submitted to the IRB as an other event.
- Relationships with clinical leadership of the Departments of Psychiatry, Obstetrics and Gynecology, and the Division of Women's Health within the Department of Medicine.

- Partnerships with colleagues at primary care and gynecology outpatient community clinics, and with Community Health Centers throughout the greater Boston area.

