- The 60-hour brexanolone vs placebo infusion will begin in the evening of the 2nd inpatient night and end on the last morning immediately preceding post-treatment assessments
- Safety assessments will be conducted daily throughout the infusion and inpatient stay
- 2 electroencephalography (EEG) recordings (one before infusion and one during the final night of the infusion)
- At least once daily assessments of rumination, attentional bias, psychomotor vigilance, mood state (POMS), and depressive symptoms (before and after the infusion)
- Daily blood draws (before and after the infusion). Blood will be collected to run assays, including brain derived neurotrophic factor (BDNF), inflammatory biomarkers, reproductive hormones, serum ALLO levels, and serum for future analyses.
- One urine collection at admission for HCG, one at morning void after first night for melatonin. If there happens to be overnight voiding on first night additional samples will be requested but there is no scheduled collection, it will only be done if the participant is awake to void on their own.

Optional post-admission MRI Visit: resting-state functional MRI (rfMRI) / magnetic resonance spectroscopy (MRS) scans (after the infusion)

Interim Follow-Up and Remote Visit: During the 1-month follow-up period after participants are discharged from the inpatient visit, participants will be asked to complete daily monitoring of their sleep, VMS, and menstrual cycle patterns.

One remote interim visit approximately 2 weeks after the inpatient visit will take place to monitor adverse events, administer the C-SSRS, and assess mood state (POMS) and depressive symptoms.

Follow-Up In-Person Visit: Approximately 30 days after treatment initiation, participants will have a final follow-up in-person visit, during which they will undergo:

- Adverse event and safety monitoring
- Optional rfMRI/MRS scanning procedures
- Behavioral assessments including depressive symptom severity, mood state (POMS), rumination, and attentional bias, psychomotor vigilance; and
- Blood draw for neuroprotective and inflammatory biomarkers, reproductive hormones, ALLO levels, and serum for future analyses.

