2. Assignment of placebo: There is a wide variability in placebo response, defined as an improvement in clinical symptoms, across patient groups. Response rates for placebo in antidepressant clinical trials range from 30% to 40% and among patients with milder forms of depression, the placebo response rate is close to 50%, at times in the range of response rates of participants assigned to the active treatment. As such, it is often argued that placebo is not “no treatment” and that participants may indeed benefit from placebo. These placebo-related risks are paralleled in the active treatment arm and will be mitigated in the same way. Specifically, potential side effects attributed to the study drug will be evaluated using the identical protocol for placebo as is used for brexanolone safety monitoring in this double-blinded trial. The infusion will be conducted on an inpatient basis, allowing for constant oversight throughout treatment exposure; after discharge we will assess mood and safety outcomes at an interim 2-week remote visit as well as at a 30-day in-person visit.

3. Treatment delay: We have mitigated the risk of delaying treatment through a short screening period and by not requiring a washout of existing medications. During the informed consent process, we will explain the alternative treatments available to each participant alongside the timeline of expected study participation. If there are exacerbations in symptoms or suicidality arises, we will ensure that the study participant receives immediate and appropriate clinical care. This may include the discontinuation of the trial for that participant.

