Analysis Plan: Briefly, primary analyses will compare exALLO and placebo subject-level response profiles from baseline to 4-day in each primary outcome to examine acute effects. Secondary analyses will compare exALLO and placebo subject-level response profiles from baseline to 30-day in those same outcomes to examine durability of effects. Analyses of secondary outcomes will be conducted in parallel with those for primary outcomes. Key covariates (e.g., age, race, body mass index, socioeconomic status and stressful events) will be measured and considered a priori as potential predictors in multivariate analyses to reduce unexplained variability. Analytic outcomes can be transformed as needed to satisfy model assumptions such as normally distributed residuals for linear models or, alternatively, non-linear distribution models (e.g., negative binomial, lognormal, or gamma) can be applied in the generalized linear mixed model approach to model the observed distribution of the outcome. Model selection will be based on Akaike information criterion or quasi-likelihood under the independence model criterion values. We will use the False Discovery Rate (FDR) correction⁴⁵, which allows for robust retention of alpha to remain at 5% for each statistical test with the additional constraint of q-threshold also set to 5% (i.e., acceptable FDR of 5%). This analytic approach is advantageous over Bonferroni adjustment and other approaches that adjust the 5% alpha threshold as it will not increase the chance of inflating Type II error given the number of primary outcomes in Aims 1 and 2.

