The primary analyses to test the hypotheses listed in Aims 1 and 2 will compare allopregnanolone and placebo subject-level response profiles from baseline to 4-day visit for each primary outcome using linear or generalized linear mixed models. Estimation of the fixed effects will allow comparison of means. Fixed effects will include treatment condition and time (baseline, 4-day, 30-day). Subject-level random effects will be modelled by including a random intercept. While linear or generalized linear mixed models provide a robust approach to handling inter-individual variability in response, we will also incorporate additional exploratory analyses to address this concern. To achieve this, we will examine our data using the interclass correlation coefficients (ICC) obtained from the R correlation matrix of the mixed-model regressions. A low ICC value will indicate that intra-individual variability in response is high relative to inter-individual variability, whereas a high ICC value will indicate that there is high inter-individual variation in response relative to intra-individual variability. Additionally, we will estimate subject-specific effects (i.e., slopes in response profiles of each subject from baseline to day 4, estimated by the random effect in the mixed models) and the distribution of subject-specific response magnitude. As exploratory analytic approaches, these subject-specific response magnitudes will be further modelled using baseline participant characteristics (e.g., age, prior history of depression) to elucidate potential physiological and neurophysiological predictors. We expect that these additional exploratory analyses will provide preliminary data on the distribution of participant-specific responses to ALLO, which will inform future studies and analyses. For **Aim 3**, the objective is two-fold: (1) we will assess mediation of improvement in clinically-defined global measures of depression severity by changes in Aim 1 and 2 outcomes, and (2) test effect modification of exogenous ALLO on improvement in clinically-defined global measures of depression severity by (i) the presence/absence of a history of depression recurrence, and separately, ii) perimenopausal factors (early vs. late perimenopause). In addition to the mediation pathways described above, we recognize that the possible pathways linking ALLO to depression are likely more numerous than these predefined mediation pathways. Therefore, we plan to further explore other putative pathways using partial least squares structural equation modeling. We will identify combinations of variables (features) that cluster together (factors) as latent variables, and then quantify the strength of their relationships based on factor loading (correlation between each feature and each factor). We will develop primary mediation models for 4-day effects and then 30-day secondary effects in

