
parallel. We will also compare mediator clustering (number of factors and combination of features) and strength of associations (factor loading) for 4-day and 30-day models to explore differences in mediation between the two time points. Comparing models at the two time points will help identify mediators that are consistent over time, indicating robustness of the findings, as well as identifying mediators that may be unique to acute and durable responses. Both vertical collinearity (predictor-predictor redundancy) and lateral collinearity (predictor-criterion) will be assessed with a variance inflation factor threshold of 3.3. Bootstrap routines will be used to determine significance of indirect effects to avoid parametric assumptions (i.e., normality). Effect size of the mediation will be assessed by Cohen's f . Assessed mediation types will include (i) full, (ii) partial mediation (complementary and competitive), (iii) only direct effect, and (iv) no effect. The significance of the difference between specific mediating effects will be assessed based on bootstrapped confidence intervals⁴⁶. 4-day and 30-day models will be tested for differences using bootstrap-based tests for overall model fit⁴⁷. To test effect modification of exogenous ALLO on improvement in clinically-defined global measures of depression severity by (i) the presence/absence of a history of depression recurrence, and separately, ii) early vs. late perimenopause, we will test for two-way interactions between each modifier with the main effect of treatment. These interaction models will be tested separately for 4-day and then 30-day effects; three-way interactions will not be tested.

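### No planned analysis uses the day-19 depression and mood scores, which can modestly attenuate the 30-day depression contrast if later dropout depends on them

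*Combined protocol and SAP*

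**What the plan says.** Section 9 (Statistical Analysis) introduces its mixed model as "The primary analyses to test the hypotheses listed in Aims 1 and 2". For that model it states "Fixed effects will include treatment condition and time (baseline, 4-day, 30-day" and "Subject-level random effects will be modelled by including a random intercept". Two further statements bear on depression scores. The first is "Analyses of secondary outcomes will be conducted in parallel with those for primary outcomes". The second concerns the Aim 3 moderation models, where depression severity is the outcome: "These interaction models will be tested separately for 4-day and then 30-day effects; three-way interactions will not be tested". The Aim 3 mediation models are likewise set for 4 days and 30 days.

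Section 6 (Interim Follow-Up and Remote Visit) has staff "administer the C-SSRS, and assess mood state (POMS) and depressive symptoms" about two weeks after the inpatient stay. The Table of Procedures puts this at day 19 ± 3. Section 7 names the HDRS-17 as the scale for repeated depression assessment, so I take that to be the measure.

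On loss to follow-up, section 4 says "We also expect to have at least 72 women complete the 30-day follow-up period", out of 80. Section 7 (Treatment delay) describes the clinical care given if symptoms worsen or suicidality arises, and adds "This may include the discontinuation of the trial for that participant". The next item in the same list provides, where feasible, a closing visit with the 30-day procedures for women who discontinue. Section 9 states no missing-data assumption.

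**The concern.** A likelihood-based mixed model handles dropout without bias when the chance of leaving depends only on scores that are in the model. After discharge, the interim visit is the only scheduled check before day 30, and it measures mood and suicidality together. A decision to stop for worsening could well follow from what is seen there. If the day-19 score drives later loss but is absent from the model, the missing 30-day scores are not missing at random given the modelled data.

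If the drug works, more placebo women will be doing badly at day 19 and more of them will leave. The women who remain on placebo then look better than the full arm would have looked, and the 30-day difference shrinks. What is at stake is the durability estimate for depression severity, and possibly for POMS, from data the trial already collects.

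**Working it through.** **1. The plan's own figure.** Inputs from section 9: 40 per arm, d = 0.64, two-sided alpha 5%. Normal approximation: power = Φ(d√(n/2) − 1.96) = Φ(0.64 × √20 − 1.96) = Φ(0.902) = 0.817. The noncentral t gives 0.807. The stated power of more than 80% reproduces.

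**2. Loss and precision at day 30.** Expected loss is at most (80 − 72)/80 = 10%, or 36 per arm if even. Power for 0.64 becomes Φ(0.64 × √18 − 1.96) = 0.775 (t: 0.764). The standard error of the difference is about √(2/36) = 0.236 SD.

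**3. Which outcomes are involved.** The Aim 1 and 2 outcomes are rumination, attentional bias, connectivity, BDNF, NAA, inflammation and WASO. Section 6 lists none of them at the interim visit. It lists adverse events, C-SSRS, POMS and depressive symptoms. The issue is therefore confined to depressive symptoms and POMS.

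**4. Bias under the planned form of model.** Large-sample simulation, 300,000 per arm, Monte Carlo error about 0.005 SD. Assumptions, none of them in the documents:
- Scores have SD 1, and means are free by arm and visit.
- Loss before day 30 is logistic in the day-19 score, with slope 1 or 2 log-odds per SD.
- Correlations are either exchangeable at 0.5, or decaying with r(19,30) = 0.7 and r(4,30) = 0.4.
- Discontinuing women supply no later score.

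Bias at 10% loss, in SD units (positive = benefit understated; RI = random intercept, UN = unstructured covariance):

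| Correlations | Effect | Slope | Dropout rule | RI, 3 times | RI, day 19 added | UN, day 19 added |
|---|---|---|---|---|---|---|
| Exchangeable | 0 | 1 | same | 0.004 | 0.004 | 0.004 |
| Exchangeable | 0.64 | 1 | same | 0.006 | −0.002 | −0.002 |
| Exchangeable | 1.0 | 2 | same | 0.023 | −0.001 | −0.001 |
| Decaying | 0 | 1 | same | 0.005 | 0.005 | 0.005 |
| Decaying | 0.64 | 1 | same | 0.021 | 0.012 | −0.001 |
| Decaying | 1.0 | 2 | same | 0.067 | 0.038 | −0.004 |
| Decaying | 0.64 | 1 | opposite by arm | 0.090 | 0.053 | 0.001 |
| Decaying | 0.64 | 2 | opposite by arm | 0.140 | 0.081 | −0.002 |

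Opposite by arm means that placebo women leave when worse and active women leave when better.

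**5. Stronger tracking between day 19 and day 30.** Here r(19,30) = 0.75–0.80 and r(4,30) = 0.40–0.50, with a true difference of 0.64, 10% loss and one dropout rule. Estimation was by maximum-likelihood regression, equivalent to unstructured covariance.
- Slope 1, 1,000,000 per arm: 0.617–0.619 without day 19, 0.639–0.643 with it.
- Slope 2, same size: 0.586–0.587 without, 0.638–0.641 with.
- Slope 2, 6,000 simulated trials of 80 women: 0.585–0.597 without, 0.641–0.645 with.

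The shift runs from 0.64 − 0.619 = 0.021 to 0.64 − 0.585 = 0.055 SD, which is 3% to 9% of the effect. Against the standard error, 0.055/0.236 = 0.23.

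**6. Precision.** If loss is purely random, adding day 19 cuts the variance of the 30-day contrast by about 3–5% at 10% loss.

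**The case against.** The strongest reply is that the quoted sentence governs other outcomes, and for those it is right. A reader might infer that the plan states it will discard the day-19 depression score. It does not: the plan is silent on that score. The link from the three-level model to depression rests on the sentence about secondary outcomes and on the Aim 3 time points, and the text never lists the HDRS-17 as a secondary outcome. This stands, and it limits the point to an unused score.

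A reader might also infer that the 30-day contrast is biased whenever women leave because of their day-19 state. The calculations do not support that. With no effect and a common rule the bias is about zero, so a false positive is not the worry in that case.

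Third, the closing visit in section 7 would recover some of the women whose loss drives the bias, whereas the simulations give them no later score. This stands in part. The visit happens only where feasible and at the time of discontinuation, and section 9 does not say how its scores enter an analysis. Day 19 also cannot help for women lost before it.

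Fourth, the figures in step 5 use unstructured covariance, whereas the plan specifies a random intercept. This matters little for the three-visit model: under decaying correlations the two give 0.021 and 0.021, or 0.067 and 0.069. It matters for the remedy, because with a random intercept alone an added day-19 level leaves 0.01 to 0.08 SD of bias when correlations decay.

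**Conclusion.** The point holds as a modest one, limited to depressive symptoms and POMS. These are measured at about day 19, no planned efficacy analysis uses the scores, and the protocol itself ties discontinuation to worsening. At the planned 10% loss and a true 0.64 SD, the 30-day depression contrast would be understated by about 0.02 to 0.055 SD, less than a quarter of its standard error. That range assumes a common dropout rule with slope 1 to 2, all modelled loss falling after day 19, and day-30 scores that track day 19 more closely than day 4. With exchangeable correlations of 0.5 and slope 1 it is only 0.006 SD. Rules that run in opposite directions by arm could raise it to 0.14 SD. It needs a real effect or arm-specific dropout.

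Two stronger readings are not supported. The day-4 primary analyses are not affected. Nor do the documents show that the mixed-model 30-day contrast feeds the Aim 3 mediation models, which are described as partial least squares structural equation models with bootstrapping.

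**What to change.** For the HDRS-17 and any other outcome measured at the interim visit, specify one likelihood model with baseline, day 4, day 19 and day 30, arm-by-visit terms, and unstructured covariance in place of the random intercept alone. Read the 30-day arm contrast from that model. State that missing scores are assumed missing at random given these visits. Enter scores from a discontinuation visit in the window in which they were actually taken, not as day-30 values. Keep the three-level factor for the outcomes that are not measured at the interim visit.

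The cost is wording in section 9, settled before unblinding, with no new visits or data. The downside is more covariance parameters (4 × 5/2 = 10, against 2 for a random intercept with residual) and a structure that differs from the one used for the other outcomes. The change does not by itself alter the partial least squares mediation models.

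### The exploratory analysis takes each woman's baseline-to-day-4 slope from a model whose only stated random effect is an intercept, so the fitted slopes cannot differ within an arm

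*Combined protocol and SAP*

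**What the plan says.** All of this is in Section 9, in the paragraph on the primary analyses for Aims 1 and 2. The listed fixed effects are treatment condition and time, with time at baseline, day 4 and day 30. On the random part the plan says: "Subject-level random effects will be modelled by including a random intercept".

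The same paragraph adds exploratory analyses of differences between women. The individual responses are to be "slopes in response profiles of each subject from baseline to day 4, estimated by the random effect in the mixed models". Their spread will be described, and "these subject-specific response magnitudes will be further modelled using baseline participant characteristics", with age and prior depression as examples. The expected product is to "provide preliminary data on the distribution of participant-specific responses to ALLO", as input to future studies.

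No random slope, subject-by-time term or separate exploratory model is stated anywhere. Covariates are mentioned only as potential predictors, without covariate-by-time terms.

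Section 6 sets the number of measurements. EEG is recorded twice, once before the infusion and once on its last night. Rumination and attentional bias are assessed at least daily in the inpatient stay, blood is drawn daily, and these measures recur at the 30-day visit. MRI is optional.

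**The concern.** A random intercept lets women differ in level. It does not let them differ in change. If the intercept is the only random effect, the quantity that the exploratory analysis is built on has no within-arm variation: there is no distribution to describe and nothing for age or prior depression to predict.

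An analyst who follows the text will find this out at analysis and will have to choose another method after seeing the data. The alternative is worse: reporting the random intercepts, which mainly reflect a woman's level, as if they were her response.

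**Working it through.** **The plan's own figure.** Section 9 claims more than 80% power at an effect size of 0.64 with 40 per arm, two-sided 5%. A two-sample t-test gives 80.7% (normal approximation 81.7%). The figure is reproduced, and the present point does not depend on it.

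**Algebra.** Write the stated model as y_ij = f(arm_i, time_j) + b_i + e_ij, with b_i the random intercept. The fitted change for woman i is

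[f(arm_i, day 4) + b_i] − [f(arm_i, baseline) + b_i] = f(arm_i, day 4) − f(arm_i, baseline).

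- Treatment and time main effects only, as listed: one value for all women.
- Treatment-by-time added: one value per arm.
- Baseline covariate main effects: these cancel as b_i does.
- Generalized model: the result holds on the link scale. With a log link the natural-scale change is exp(b_i) × [exp(η_4) − exp(η_0)], with η the fixed part. It differs between women only through their level. For example, η falling from 1.0 to 0.6 gives every woman the same ratio, exp(−0.4) = 0.67.

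**Numerical check.** One simulated data set, with assumed values because the documents give no variances: 80 women, three visits, intercept SD 1, residual SD 0.6, individual change truly related to age, realised SD of true change 0.85. REML fits gave:

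| Model | Distinct fitted slopes | Within-arm SD |
|---|---|---|
| Random intercept, treatment + time | 1 (−0.94) | about 1e-16 |
| Random intercept, treatment × time | 2 (−0.42 and −1.46) | about 1e-16 |
| As above, plus age | 2 | about 1e-16 |
| Random intercept and random post-baseline change, treatment × time | 80 | 0.60 and 0.71 |

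In the first two models the predicted intercepts correlated 0.83 with true level and 0.44 with true change. In the last model the fitted slopes correlated 0.78 with true change.

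**Can a random change term be estimated?** Let the intercept variance be B, the change variance C, their covariance K and the residual variance R.

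- Two measurements give three moments: B + R, B + K, and B + 2K + C + R. Four unknowns cannot be solved from three equations. Setting K = 0 makes it three for three.
- Three measurements with change coded 0/1/1 also give the covariance of the two later values, B + 2K + C. All four unknowns then follow, provided R is the same at every visit.

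**One variance or two?** If true change varies with SD 0.6 in the exALLO arm and not at all in placebo, a pooled variance with equal arms averages to (0.36 + 0)/2 = 0.18, an SD of 0.42. Simulations with a pooled variance gave median estimates of 0.38 to 0.47 against the true 0.6.

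**Observed change.** Its variance is C + 2R. For assumed R of 0.3, 0.5 and 0.7 the SD is √(0.36 + 2R) = 0.98, 1.17 and 1.33 when true change has SD 0.6. It is √(2R) = 0.77, 1.00 and 1.18 when true change does not vary at all.

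**Precision of interactions.** For a two-level characteristic with proportion p, 40 per arm, the standard error is √{2[1/(40p) + 1/(40(1−p))]} residual SD. With p = 0.5 (assumed) this is √0.20 = 0.447. At 80% power, two-sided 5% (noncentral t, multiplier about 2.84), the detectable interaction is 1.27 residual SD, twice the 0.63 for the treatment main effect. With p = 0.7 (assumed) it is 1.38. For a continuous characteristic such as age, √(2/39) gives 0.64 per SD.

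**The case against.** The strongest reply is that the random-intercept sentence describes the primary model, while the slope sentence belongs to additional exploratory work and, by speaking of slopes from a random effect, implies a random slope. That is a fair guess at the intention. It does not settle the matter, because the term is not written and adding it is more than wording. It cannot be estimated with free covariance for wake after sleep onset, and its time coding, covariance and variance by arm all affect the answer.

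It is also fair to say that the analysis is exploratory and that the data can support it. Both stand. Three stronger readings should be resisted:

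- A reader might infer that the primary treatment comparison is compromised. It is not: comparing arm means does not use individual slopes.
- A reader might infer that individual change can be studied only through the 30-day visit. Section 6 plans repeated inpatient assessments and blood draws, which can serve where they exist.
- A reader might count the sentence on intraclass correlation as a second error, since it says "a high ICC value will indicate that there is high inter-individual variation in response relative to intra-individual variability". If response there means the outcome value, this is a standard description of the coefficient. The text does not show that response to ALLO is meant, so no error is established.

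**Conclusion.** The point holds. As written, the plan yields one fitted slope for all women, or one per arm if treatment-by-time is included, with within-arm SD of zero. This is algebra and needs no assumption about variances; the simulated values only illustrate it. It would fail only if the model had a random slope, a time-varying covariate or a covariate-by-time term, and none is stated.

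The consequence is confined to the exploratory description and prediction of individual response. The plan should be corrected, at a priority suited to an exploratory analysis. The figures for pooled variance, observed change and interaction precision rest on assumed variances or splits and indicate scale only.

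**What to change.** Change the exploratory paragraph of Section 9 only.

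1. Individual change, by one of two routes:
   - (a) For outcomes with at least three measurements, using day 30 or the repeated inpatient values where these exist, add a subject-level random change term. State its time coding, its covariance with the intercept, and a separate variance for each arm. State also the reliance on equal residual variance across visits.
   - (b) Use observed baseline-to-day-4 change, displayed by arm, and say that it includes measurement error and change not due to the drug.
2. Wake after sleep onset: with two recordings, use observed change, or state openly the restrictive assumption of zero covariance.
3. Predictors of response to ALLO: replace the regression of slopes with treatment-by-characteristic interactions on the day-4 value adjusted for baseline. Keep to the outcomes and characteristics that this paragraph already covers, label the results exploratory and give 95% intervals. Section 9 already plans interactions of this kind for depression severity in Aim 3.
4. Say that these estimates will be imprecise: about 1.27 residual SD for 80% power at an even split, more for uneven splits, and more again for the optional MRI outcomes, where fewer women will contribute.

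The cost is one paragraph of text and a little programming. It needs no new data, visits or participants.
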